11.0 Study Timelines

11.1 Describe the anticipated duration needed to enroll all study subjects.

Response: Enrollment of 90 patients should be completed within 10 months at a rate of 9 patients/month.

*11.2 Describe the duration of an individual subject's participation in the study.
Include length of study visits, and overall study follow-up time.*

Response: 52 Weeks

*11.3 Describe the estimated duration for the investigators to complete this study
(i.e. all data is collected and all analyses have been completed).*

Response: Approximately 30 Months

12.0 Setting

*12.1 Describe all facilities/sites where you will be conducting research procedures.
Include a description of the security and privacy of the facilities (e.g. locked facility, limited access, privacy barriers). Facility, department, and type of room are relevant. Do not abbreviate facility names.*

NOTE: Examples of acceptable response may be: "A classroom setting in the Department of Psychology equipped with a computer with relevant survey administration software," "The angiogram suite at Buffalo General Medical Center, a fully accredited tertiary care institution within New York State with badge access," or, "Community Center meeting hall."

Response: Research will be conducted at the Diabetes Endocrinology Research Center of WNY, located at [name] and at the CTRC located in [name]. The Diabetes Research Center has facilities and exam rooms available for insulin pump download, CGM device download, meal and infusion studies and presence of study coordinator and registered nurse for data collection and blood work at all times. One of the investigators will be available at all times to address patients' related issues. CTRC location is a fully equipped laboratory with equipment include ultra-low freezers for sample storage, centrifuges, microscopes for sample preparation, infusion pumps, ELISA, PCR and immunoblotting instrumentation.

12.2 For research conducted outside of UB and its affiliates, describe:

- *Site-specific regulations or customs affecting the research*
- *Local scientific and ethical review structure*

NOTE: This question is referring to UB affiliated research taking place outside UB, i.e. research conducted in the community, school-based research, international research, etc. It is not referring to multi-site research. UB affiliated institutions include Kaleida Health, ECMC, and Roswell Park Cancer Institute.

Response:

N/A: This study is not conducted outside of UB or its affiliates.

13.0 Community-Based Participatory Research

13.1 Describe involvement of the community in the design and conduct of the research.

NOTE: Community-Based Participatory Research (CBPR) is a collaborative approach to research that equitably involves all partners in the research process and recognizes the unique strengths that each brings. CBPR begins with a research topic of importance to the community, has the aim of combining knowledge with action and achieving social change to improve health outcomes and eliminate health disparities.

Response:

N/A: This study does not utilize CBPR.

13.2 Describe the composition and involvement of a community advisory board.

Response:

N/A: This study does not have a community advisory board.

14.0 Resources and Qualifications

*14.1 Describe the qualifications (e.g., education, training, experience, expertise, or certifications) of the Principal Investigator **and** staff to perform the research.*

When applicable describe their knowledge of the local study sites, culture, and society. Provide enough information to convince the IRB that you have qualified staff for the proposed research.

NOTE: If you specify a person by name, a change to that person will require prior approval by the IRB. If you specify a person by role (e.g., coordinator, research assistant, co-investigator, or pharmacist), a change to that person will not usually require prior approval by the IRB, provided that the person meets the qualifications described to fulfill their roles.

Response: All study personnel are educated, trained, and licensed as required for their delegated role in this study. All study personnel have also received the required university training and will be trained by the PI before the study starts

Describe other resources available to conduct the research.

14.2 Describe the time and effort that the Principal Investigator and research staff will devote to conducting and completing the research.

NOTE: Examples include the percentage of Full Time Equivalents (FTE), hours per week. The question will elicit whether there are appropriate resources to conduct the research.

Response: The principal investigator supervises the research project and weekly research meetings are conducted to discuss the recruitment rate, resolve and discuss issues related to the conduct, safety, analysis of the study and related publications. PI is expected to spend 5% of his academic time on this research. The co-investigators and study coordinator provide coverage to the research related activity for 365 days a year.

14.3 Describe the availability of medical or psychological resources that subjects might need as a result of anticipated consequences of the human research, if applicable.

NOTE: One example includes: on-call availability of a counselor or psychologist for a study that screens subjects for depression.

Response: Available medical literature will be provided as deemed appropriate or requested by patient through UB libraries, PubMed, Google scholar as all the investigators have access to medical literature through listed resources above. The patient will also have access to physician (Investigators and Co-Investigators) who will be available to address any adverse effects or other questions during the course of the study and make the appropriate referrals.

14.4 Describe your process to ensure that all persons assisting with the research are adequately informed about the protocol, the research procedures, and their duties and functions.

Response: Education through training meetings, conferences and discussions. Training records will be kept by study coordinator and updated when following any amendments

15.0 Other Approvals

15.1 Describe any approvals that will be obtained prior to commencing the research (e.g., school, external site, funding agency, laboratory, radiation safety, or biosafety).

Response: NA

N/A: This study does not require any other approvals.

16.0 Provisions to Protect the Privacy Interests of Subjects

16.1 Describe how you will protect subjects' privacy interests during the course of this research.

NOTE: Privacy refers to an individual's right to control access to him or herself. Privacy applies to the person. Confidentiality refers to how data collected about individuals for the research will be protected by the researcher from release. Confidentiality applies to the data.

Examples of appropriate responses include: "participant only meets with a study coordinator in a classroom setting where no one can overhear", or "the participant is reminded that they are free to refuse to answer any questions that they do not feel comfortable answering."

Response:

When the patient is being seen at our outpatient clinics for the first time they sign the "Consent to use and disclosure of protected health information" form which clearly states that their protected health information (PHI) can be used for review in preparation for possible research.

Our clinical providers involved in the study will identify potential patients for recruitment from the Diabetes-Endocrinology Center of WNY Clinics according to the inclusions and

exclusion criteria and through advertisements. Patient who may qualify will be asked in private during their one on one consultation time with the physician if they wish to participate in the research study. If the patient agrees, the research coordinator will contact them for a telephone screening interview privately. During phone conversation, no private information will be spoken loudly by study staff conducting the interview. The patients who call for potential participation in the study due to advertisement flyers will be screened over the phone with the research coordinator, using our telephone screening form. All records of this telephone interview will be kept in the study binder locked in the research unit.

If the patient passes the telephone screening, they will be asked to make an appointment to review the consent. Patient will do this in a private, screen off area of the research department and will be allowed to discuss the consent in detail with the research coordinator and or study doctor. Patient will be notified that it is completely voluntary to participate in the research study and can withdraw at any time.

We will not be accessing any medical information of the patients for whom the services are not provided by our clinic providers.

16.2 Indicate how the research team is permitted to access any sources of information about the subjects.

*NOTE: Examples of appropriate responses include: school permission for review of records, consent of the subject, HIPAA waiver. This question **does apply** to records reviews.*

Response: Consent of the subject and partial HIPAA waiver.

17.0 Data Management and Analysis

17.1 Describe the data analysis plan, including any statistical procedures. This section applies to both quantitative and qualitative analysis.

Response: **DATA ANALYSIS**

This is a prospective study to evaluate effect of Exenatide extended release treatment for 1 year on albuminuria levels in T2DM patients with micro- and macroalbuminuria compared to placebo. The similarities in baseline values between the study groups will be compared using appropriate parametric tests. Transformations of the data on order to meet statistical assumptions may be considered. All statistical analysis will be carried out using SPSS software (SPSS Inc, Chicago, Illinois) based on intention to treat principle. Data will be presented as mean±standard error. The primary endpoint of the study is the change from baseline in albuminuria level at weeks 12, 26, 39 and 56 following Exenatide extended release and placebo treatments. Fasting samples collected at weeks 0, 12, 26, 39 and 56 will be used for this assessment with values at week 0 considered as baseline. Changes from baselines from both drugs arms will be compared to those from the placebo arms in both the micro and macroalbuminuria groups. The statistical analysis will be done using mixed model for repeated measurement (MMRM) analysis with assigned α value of 0.05. Our preliminary data on retrospective analysis of the difference in albuminuria following GLP-1RA treatment for 2.5 yrs in T2DM patients with micro and macroalbuminuria show regression of albuminuria (UACR) by approximately 55mg/mg and 500mg/g (about 50% reduction), respectively.

The secondary end points include the comparison of the changes in albuminuria based on baseline albuminuria category (micro or macro), creatinine clearance, Cystatin C, TGF β , type I and IV collagen, CTGF, and fibronectin levels, the expression of SMAD3, SMAD4, NQO-1, GST-1P and HO-1, Nrf-2/keap-1 system activation between the Exenatide extended release and placebo groups and across albuminuria categories

17.2 If applicable, provide a power analysis.

NOTE: This may not apply to certain types of studies, including chart/records reviews, survey studies, or observational studies. This question is asked to elicit whether the investigator has an adequate sample size to achieve the study objectives and justify a conclusion.

Response: Conservatively estimating a difference in the change from baseline in albuminuria after 1 year between the Exenatide extended release and placebo groups (across both albuminuria groups) of 60mg/g, with standard deviation of no more than 91mg/g, a sample size of 38 patients per group should provide adequate power ($\beta = 0.2$) to detect a significant difference ($\alpha = 0.05$). Assuming a drop-out rate of 15% and 2:1 drug: placebo randomization ratio, 60 active and 30 control will be recruited for a total of 90 patients (rounded up). Patients will be enrolled based on a predetermined stratification according to the two albuminuria categories (micro and macro at 1:1 ratio) with 45 patients in each.

17.3 Describe any procedures that will be used for quality control of collected data.

Response: Three investigators and research nurse will double check the accuracy of collected data. All laboratory testing will be standardized using references and standards.

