This is a prospective study to evaluate effect of Exenatide extended release treatment for 1 year on albuminuria levels in T2DM patients with micro- and macroalbuminuria compared to placebo. The similarities in baseline values between the study groups will be compared using appropriate parametric tests. Transformations of the data on order to meet statistical assumptions may be considered. All statistical analysis will be carried out using SPSS software (SPSS Inc, Chicago, Illinois) based on intention to treat principle. Data will be presented as mean±standard error. The primary endpoint of the study is the change from baseline in albuminuria level at weeks 12, 26, 39 and 56 following Exenatide extended release and placebo treatments. Fasting samples collected at weeks 0, 12, 26, 39 and 56 will be used for this assessment with values at week 0 considered as baseline. Changes from baselines from both drugs arms will be compared to those from the placebo arms in both the micro and macroalbuminuria groups. The statistical analysis will be done using mixed model for repeated measurement (MMRM) analysis with assigned α value of 0.05. Our preliminary data on retrospective analysis of the difference in albuminuria following GLP-1RA treatment for 2.5 yrs in T2DM patients with micro and macroalbuminuria show regression of albuminuria (UACR) by approximately 55mg/mg and 500mg/g (about 50% reduction), respectively. Conservatively estimating a difference in the change from baseline in albuminuria after 1 year between the Exenatide extended release and placebo groups (across both albuminuria groups) of 60mg/g, with standard deviation of no more than 91mg/g, a sample size of 38 patients per group should provide adequate power ($\beta = 0.2$) to detect a significant difference ($\alpha = 0.05$). Assuming a drop-out rate of 15% and 2:1 drug:placebo randomization ratio, 60 active and 30 control will be recruited for a total of 90 patients (rounded up). Patients will be enrolled based on a predetermined stratification according to the two albuminuria categories (micro and macro at 1:1 ratio) with 45 patients in each.

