The secondary end points include the comparison of the changes in albuminuria based on baseline albuminuria category (micro or macro), creatinine clearance, Cystatin C, TGF β , type I and IV collagen, CTGF, and fibronectin levels, the expression of SMAD3, SMAD4, NQO-1, GST-1P and HO-1, Nrf-2/keap-1 system activation between the Exenatide extended release and placebo groups and across albuminuria categories.

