10.0 Procedures Involved

10.1 Provide a description of **all research procedures or activities** being performed and when they are performed once a subject is screened and determined to be eligible. Provide as much detail as possible.

NOTE: This should serve as a blueprint for your study and include enough detail so that another investigator could pick up your protocol and replicate the research. For studies that have multiple or complex visits or procedures, consider the addition of a schedule of events table in in your response.

Response:

Visit 1 (week 0):

Qualifying subjects will be asked to come for the visit in a fasting state (10-12 hr fasting), vitals will be done and safety labs for CBC, CMP, HbA1C, kidney function tests will be drawn and 24hr urine will be collected. Blood samples (30ml) will be collected for research endpoints. Training on administrating study drug and information about side effects and how to report any adverse events will be discussed with patients. One of the treatment arms will be administered to the patient (placebo or Exenatide extended release in a randomized fashion) and enough drug supply for 13+2 weeks will be dispensed. Other diabetes medications will be reviewed and any standard of care adjustments will be made. A 24hr urine collection container will be dispensed and patients will be instructed to come back after 13 weeks.

Visits 2, 3 and 4 (Weeks 13, 26 and 39):

Patients will come to this visit in the fasting state. Physical exam (only on visit 3) and vitals will be performed, safety labs for CBC, CMP, HbA1c, kidney function tests will be drawn and 24hr urine collected. Blood samples (30ml) will be collected for research endpoints. Other diabetes medications will be reviewed and any standard of care adjustments will be made. Study medication use compliance will be assessed and drug supply for 13+2 weeks will be dispensed. A 24hr urine collection container will be dispensed and patients will be instructed to come back after 13 weeks.

Visit 5 (Week 52): Patients will come to this visit in the fasting state. Physical exam and vitals will be performed, safety labs for CBC, CMP, HbA1c, kidney function tests will be drawn and 24hr urine collected. Blood samples (30ml) will be collected for research endpoints. Other diabetes medications will be reviewed and any standard of care adjustments will be made. Patient will be discharged from the study after the final safety phone call at week 56.

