The study investigations include evaluation of the effects of 1-year treatment with Exenatide extended release or placebo on progression of albuminuria and related kidney function measures in T2DM patients with established micro- or macroalbuminuria. Qualified patients will come fasting to the research center. Review of study procedures and vitals will be performed. Basal blood and 24-urine samples will be obtained. Patients will be randomized (in 2:1 ratio) to receive either Exenatide extended release or placebo for 1 year. Plasma and mononuclear cell (MNC) fractions will be prepared from the blood samples. Additional fasting blood and 24hr urine samples will be collected every 13 \pm 2 weeks (3, 6, 9 and 12 months) for a total of 5 study visits. Measurements of albuminuria, creatinine, creatinine clearance, GFR, isoprostanes and cystatin C following 1-year treatment with Exenatide extended release or placebo will be done on all urine samples collected before and at 3, 6, 9 and 12 months following treatment with Exenatide extended release or placebo. HbA1c, CBC, CMP, TGF β , type I and IV collagen, CTGF, PAI-1, TIMP-1 and 2 and fibronectin EDA levels will be measured in all plasma samples collected while the expression of SMAD3, SMAD4, NQO-1, GST-1P and HO-1, Nrf-2/keap-1 system activation, p47^{phox} levels and ROS generation will be done in all MNC samples collected before and at 13, 26, 39 and 62 weeks following treatment with Exenatide extended release or placebo.

Visit #	Screening	1	2	3	4	5
Weeks #	<-4	0	13 \pm 2	26 \pm 2	39 \pm 2	52 \pm 2
Medical History	X					
Physical exam	X			X		X

CBC/CMP/kidney function	X	X	X	X	X	X
Vitals and BP	X	X	X	X	X	X
Pregnancy test	X		X	X	X	X
HbA1c	X	X	X	X	X	X
MNC endpoints		X	X	X	X	X
Plasma mediators endpoints		X	X	X	X	X
Urinary endpoints		X	X	X	X	X
Other diabetes medications review and adjustments		X	X	X	X	X

 10.3 List any instruments or measurement tools used to collect data (e.g. questionnaire, interview guide, validated instrument, data collection form).

Include copies of these documents with your submission.

Response: Source documents will be used to collect patient information. Food and glucose measurement diaries will be also reviewed for medication adjustment.

10.4 Describe any source records that will be used to collect data about subjects (e.g. school records, electronic medical records).

Response: electronic medical records and research files.

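### The primary text names no single decisive contrast: it lists four visits and compares arms in both albuminuria strata at one alpha of 0.05, while the trial is sized on one pooled 1-year difference.

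*Combined protocol and SAP*

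**What the plan says.** **Primary endpoint.** Section 17.1, in text that 2.1 repeats, reads "The primary endpoint of the study is the change from baseline in albuminuria level at weeks 12, 26, 39 and 56". Both sections add: "Fasting samples collected at weeks 0, 12, 26, 39 and 56 will be used for this assessment". The comparison is given as "Changes from baselines from both drugs arms will be compared to those from the placebo arms in both the micro and macroalbuminuria groups". The method is an MMRM with an alpha of 0.05. No visit is singled out, no pooled test is named and there is no multiplicity rule.

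**Urine schedule.** Section 10.1 collects 24-hour urine at weeks 0, 13, 26 and 39, and last at "Visit 5 (Week 52): Patients will come to this visit in the fasting state". The table in 10.2 gives each post-baseline visit a window of ±2 weeks, and the text there counts "3, 6, 9 and 12 months) for a total of 5 study visits". Week 56 appears in 10.1 only as a telephone contact: "Patient will be discharged from the study after the final safety phone call at week 56".

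**Sample size.** Section 17.2 sizes the trial on the "difference in the change from baseline in albuminuria after 1 year between the Exenatide extended release and placebo groups (across both albuminuria groups"), set at 60 mg/g with an SD of at most 91 mg/g.

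**Secondary endpoints.** Section 2.1, and again 17.1, state "The secondary end points include the comparison of the changes in albuminuria based on baseline albuminuria category (micro or macro").

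**Groups.** Section 4.1 plans 30 exenatide and 15 placebo patients in each stratum.

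**The concern.** An MMRM is a model, not a hypothesis. One fit can give a treatment effect averaged over visits, a treatment-by-visit test, a contrast at any single visit, or any of these within a stratum. The primary text does not say which of them decides the trial, and its one sentence on the comparison points to the strata. Only one drug is under test, so the plural reference to drug arms most naturally means the exenatide group in each stratum of section 4.1, each set against its own placebo group. The sizing points to a single pooled comparison at 1 year. The secondary list takes the by-stratum comparison out of the primary altogether.

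The primary result could therefore be read as a pooled test, a test in either stratum, a test required in both strata, or a test at any listed visit. These readings differ in power and in error rate, and the trial was sized for only one of them. If the choice is made once data have been seen, the 5% level does not cover it.

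**Working it through.** **1. Week labels.** The last urine window closes at 52 + 2 = week 54, so week 56 lies 2 weeks outside it. The first post-baseline window opens at 13 − 2 = week 11, so week 12 lies inside it. Five samples are named and five visits collect urine, and they match one to one.

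**2. The plan's own sample size.** Inputs from 17.2: difference 60 mg/g, SD 91 mg/g, alpha 0.05, power 0.80. The plan does not state sidedness; two-sided is assumed.

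n per arm = 2 × (1.96 + 0.8416)² × 91² / 60² = 36.1, so 37. With the t distribution it is 38 (power 81.0%). A one-sided test would need 29. Inflation: 76 / 0.85 = 89.4, so 90. The stated 38 and 90 are thus reproduced as one two-sided test, 1:1, at the full 0.05. The sizing covers a single contrast.

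**3. Power of the candidate contrasts.** Noncentral t, two-sided 0.05, with SE = SD × √(1/n₁ + 1/n₂) and noncentrality = 60 / SE.

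| Contrast | n₁ v n₂ | SD (mg/g) | SE | 60 / SE | Power |
|---|---|---|---|---|---|
| Pooled, no drop-out | 60 v 30 | 91 | 20.35 | 2.95 | 83.1% |
| Pooled, after 15% drop-out | 51 v 25.5 | 91 | 22.07 | 2.72 | 76.5% |
| One stratum, pooled inputs | 30 v 15 | 91 | 28.78 | 2.09 | 53.1% |
| Micro, GLP-1RA users' SD | 30 v 15 | 64.5 | 20.40 | 2.94 | 82.0% |
| Macro, GLP-1RA users' SD | 30 v 15 | 606 | 191.6 | 0.31 | 6.1% |

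The last two SDs are those of UACR change in the retrospective GLP-1RA users in section 3.1. The normal approximation gives 83.9% for the first row and 77.6% for the second. The second row falls short of 80% because 38 per group is a 1:1 figure: at 2:1 the same inputs need 56 + 28 = 84 evaluable patients, and 84 / 0.85 = 98.8, so 99 enrolled.

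**4. False positives if any listed comparison could count.** The plan states no such rule, so this only shows what the wording leaves open. Each test is at two-sided 0.05, with equally correlated statistics across visits and independent strata. The documents give no between-visit correlation; 0.5 to 0.9 is assumed. The value 0.5 is what changes from a shared baseline have when visits have equal variance and equal pairwise correlation.

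| Family | Correlation 0.5 | 0.7 | 0.9 |
|---|---|---|---|
| Four visits, pooled | 15.6% | 13.0% | 9.4% |
| Four visits × two strata | 28.7% | 24.4% | 17.8% |

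Either stratum at one visit: 1 − 0.95² = 9.75%. One named contrast: 5%.

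**The case against.** The strongest reply is that the intended test is clear enough. Aim 1.1 and Hypothesis 1, the only hypothesis not marked exploratory, do not separate the strata. The aim and the sizing both refer to 1 year, the sizing pools both groups, and the by-category comparison is listed as secondary. What remains is one loose sentence and an unnamed visit. Much of this stands: the pooled 1-year contrast is the best inference. It is still only an inference, and the sentence that defines the primary comparison points elsewhere.

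Three stronger readings are tempting, and the documents do not support them.

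- *A reader might infer that the final primary measurement will not be collected.* Urine is collected at week 52, and the five samples pair with the five visits. Week 56 is a wrong label.
- *A reader might infer that the plan runs eight unadjusted tests with an error rate near 29%.* The plan does not say that separate tests will be run or that any one of them counts as success, and its MMRM could deliver one overall treatment test.
- *A reader might infer that power within a stratum is 53%, and 0.531² = 28% if both must succeed.* That assumes 60 mg/g and SD 91 in each stratum. Section 3.1 contradicts a common SD: 64.5 and 606 mg/g in users, 201 and 2085 mg/g in non-users.

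**Conclusion.** The point holds. The primary comparison as written in 2.1 and 17.1 contradicts both the sizing and the secondary list, and nothing else in the documents settles which result decides the trial. This needs fixing before unblinding, because a choice made afterwards cannot be credibly defended at the 5% level.

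The pooled week 52 contrast is the one the trial was sized for. Its power is 83% with every patient evaluable and about 77% after the plan's own drop-out, so the stated 80% needs restating. That rests on the plan's 60 and 91 mg/g, a two-sided test and equal drop-out in the arms. It is a simple two-group calculation that takes no account of any gain from the repeated measures. Within-stratum power cannot be pinned down. It runs from about 6% to 82% across the users' SDs, if the difference is 60 mg/g in each stratum and nobody drops out. The range of 9% to 29% for false positives illustrates what open wording permits and is not a rate the plan states. The week labels alone would be an editorial matter.

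**What to change.** In 2.1 and 17.1:

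- Replace weeks 12 and 56 with the urine visits of section 10, giving weeks 13, 26, 39 and 52.
- State one primary contrast: exenatide minus placebo in change from baseline in albuminuria at the week 52 visit, pooled over strata, from one MMRM with albuminuria stratum as a factor, at two-sided 0.05.
- Delete the by-stratum comparison from the primary text. List the earlier visits and the within-stratum contrasts as secondary.
- If another contrast is intended, such as the effect averaged over visits, state it and base the sample size on it.

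In 2.1 and 17.2, restate the power for 2:1 allocation after drop-out: about 77% with 90 enrolled. Section 10.2 has a similar slip, giving week 62 for the last mononuclear-cell sample, and it can be corrected at the same time.

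Naming the sized contrast changes wording only; visits and design stay as they are. Keeping a full 80% after drop-out would be a separate decision, needing about 99 enrolled under the same inputs. The sponsor gives up the option of claiming the primary result from an early visit or from a single stratum.
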